#### 5.3.7 *Unscheduled/safety Visits*

During the all treatment and the follow-up period, the Investigator may conduct unscheduled visit that may perform again study procedures, including vital signs assessments, blood sample taken and physical examination. These visits will have to be motivated by the Investigator in the aim of guarantee the safety of the patients.

Specific events listed bellow, will automatically generate an Unscheduled/safety visit:

- ALT increase of 2 times of the baseline value at V0: A safety visit has to be performed 15 days later. A blood taken will be performed to check the ALT level.
- ALT increase of 5 times the upper limit of the normal range (ULN): A safety visit has to be performed 15 days later. A blood taken will be performed to check the ALT level

Please refer to paragraph 10 for withdrawal criteria.

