### 4.1 Study Design

The study is a three arm (placebo, lanifibranor 800 and 1200 mg/day), randomized (1:1:1), double-blind, placebo-controlled, multicenter, 24-week treatment study.

The goal of the proposed study is to show improvement of cardinal NASH histopathologic features as well as safety data after a 6-month treatment.

The study will require to randomize 225 NASH patients (*i.e.* at least 300 screened patients, see section 9.2 for sample size description). The overall study design is shown in Figure 1.

Patients will undergo 6 visits: screening visit (V-1, -8 weeks to -2 weeks), randomization (V0), interim visit 1 (V1, 4 weeks after V0), interim visit 2 (V2, 10 weeks after V1), End of treatment visit (V3, 10 weeks after V2) and a follow-up visit (4 weeks after V3). A detailed list of procedures performed at each visit is presented in section 5.

As the main efficacy goal of the study is to assess treatment effect on histologic features of NASH, there will be a centralized reading of slides of a liver biopsy to confirm the diagnosis and assess the severity at screening phase (V-1) and end of treatment visit (V3). At the screening phase, the liver biopsy could either have been performed within 6 months before the screening period or performed during the screening process after confirmation of the patient eligibility regarding all others inclusion/exclusion criteria (incl. biological values, physical examination, ECG, FibroScan, and LMS in selected centers). The liver biopsy at the end of the treatment period will be performed as part of the visit 3 (week 24).

Clinical and laboratory safety assessments will be performed at each visit. ECG will be performed at screening, interim visit 1 and end of treatment and will be read centrally.

A FibroScan™ will be performed at screening and end of treatment visit to assess Transient Elastography (TE) and Controlled Attenuation Parameter (CAP).

Inflammatory, glucose metabolism and lipid metabolism markers will also be assessed as well as exploratory biomarkers of NASH activity or PPARs agonist activities.

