### 5.3.3 Randomization and Beginning of the Treatment Period (V0)

At this visit, the eligibility of the patient is confirmed, and the treatment starts.

The assessments to be performed are listed in the Schedule of Study Procedures (Table 1).

Blood sampling: Kits with supplies and instructions are provided for the safety, efficacy, biobank, pharmacokinetics and genotype blood sampling as early as possible in the morning. Blood samples will be taken in the morning after overnight fasting. The patient must be fasting overnight from 10:00 pm. Alternatively, blood sampling can be performed in the afternoon provided patients have been fasting for at least eight hours.

Safety: AEs that have occurred since the last visit are recorded, irrespective of a potential relationship with the concomitant background treatment. Please observe the reporting requirements for AEs (see Section 6).

Randomization: The randomization code is provided through an online system after identification with a login and a password. Once some details are entered, the system lets you know immediately, which medication kit to use for this particular patient.

Treatment: The patient receives one monthly kit (packaging described in Figure 4), and they are carefully instructed how to take the drug and the importance of bringing back to the site the unused medication at each visit. Patients need to take morning 3 tablets with food, i.e. one tablet from each of the containers A, B, and C.

The date of the next visit in 4 weeks is agreed. The time window for the visits is +/- 3 days.

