## **10. Patient Withdrawal & Replacement**

### **10.1 Patient Withdrawal**

Participation in the study is strictly voluntary. The patients have the right to withdraw from the study at any time for any reason, without the need to justify. The Investigator also has the right to withdraw patients in case of safety concerns, protocol deviations or administrative reasons. Since an excessive rate of withdrawals can render the study uninterpretable, the unnecessary withdrawal of patients must be avoided.

Reasons of withdrawal include, but are not limited, to the following:

- Patient decision
- Lost to follow-up, death

- Any AE, laboratory abnormality or illness which, in the opinion of the Investigator, indicates that continued treatment with study therapy and participation in the trial is not in the best interest of the subject.
- Major protocol deviation: e.g. lack of compliance with scheduled visits, non-compliance with study treatment, treatment with prohibited medication during the study (see 22)
- Any deterioration in cardiac status
- ALT or AST > 8 x ULN; or if ALT or AST > 5xULN for more than 2 weeks; or if ALT or AST > 3xULN and bili (total) > 2xULN (or INR>1.5); or ALT or AST > 3xULN and symptoms (Right Upper Quadrant pain, nausea, ...)
- Investigator's decision for any other reason

If a patient discontinues the study, the Investigator will make reasonable efforts to obtain the reason and to perform all protocol-defined end of study assessments as soon as possible. The reason and circumstances for premature discontinuation (e.g. consent withdrawal, AE, lost to follow up, etc.), and the date of withdrawal must be documented in the eCRF. If a patient discontinues the study for safety reasons, the outcome must be known.

In the case of withdrawal due to pregnancy (see paragraph 6.2.1), the patient will be followed until outcome, i.e. at least on a quarterly basis for follow-up evaluation of the pregnancy, foetus, delivery and new born. In the case of withdrawal due to an AE the patient will be followed until resolution of the AE, or until in the opinion of the Investigator the event has stabilized, and the patient is referred to their primary physician for appropriate management of the ongoing event. Reasonable efforts will be made to contact a patient who fails to attend any follow-up appointments, in order to ensure that he/she is in satisfactory health.

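### The mandated 15-day liver recheck covers ALT only, so the withdrawal reason of AST above 5xULN for more than 2 weeks has no timed second sample for about 70 days after V1 or V2

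*Protocol*

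**What the plan says.** Protocol section 5.3.7 lets the investigator hold unscheduled visits and names two events that generate one automatically. The first is "ALT increase of 2 times of the baseline value at V0: A safety visit has to be performed 15 days later". The second is "ALT increase of 5 times the upper limit of the normal range (ULN): A safety visit has to be performed 15 days later". For both, the stated laboratory action is the same: "A blood taken will be performed to check the ALT level". The section then sends the reader to section 10 for the withdrawal criteria.

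Section 10.1 lists liver-related reasons for withdrawal, and every one is written for either transaminase. The peak and persistence limbs read "ALT or AST > 8 x ULN; or if ALT or AST > 5xULN for more than 2 weeks". The combined limb begins "ALT or AST > 3xULN and bili (total) > 2xULN (or INR>1.5", and a further limb joins a level above 3xULN to symptoms.

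Section 4.1 sets the schedule after V1: "interim visit 2 (V2, 10 weeks after V1), End of treatment visit (V3, 10 weeks after V2". Section 5.3.3 adds "The time window for the visits is +/- 3 days", and the schedules of procedures refer these windows to V0. The protocol's Table 1 puts AST, ALT, total bilirubin and INR at every scheduled visit.

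**The concern.** A persistence criterion needs two measurements separated by at least the stated time. Section 5.3.7 looks designed to supply the second one. It shares the 5xULN level with section 10.1, it points to section 10, and its 15-day interval is just long enough to show that an elevation has lasted more than 14 days. But it does this for ALT only, while section 10.1 treats ALT and AST as interchangeable. The protocol gives no reason for the difference.

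Two patients at the same multiple of ULN would therefore be followed differently depending on which transaminase leads. For the ALT-led patient the protocol orders a sample that can settle whether the criterion is met. For the AST-led patient it orders none before the next scheduled visit. Entry criteria do not rule this patient out: inclusion criterion 4 caps ALT at below 10xULN and sets no AST limit. What is at stake is whether one of the protocol's own liver-safety withdrawal reasons can be applied in time. Sample size, power and type I error are not affected.

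**Working it through.** **Inputs.** Scheduled visits are at weeks 0, 4, 14, 24 and 28 (Table 1 and section 4.1). The window is 3 days either side of target (section 5.3.3). The automatic recheck comes at 15 days (section 5.3.7). The persistence limit is more than 2 weeks, i.e. 14 days (section 10.1).

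**The plan's own interval.**
- V1 to V2: (14 − 4) × 7 = 70 days.
- V2 to V3: (24 − 14) × 7 = 70 days.

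Both match the 10 weeks stated in section 4.1. With a 3-day window at each end, the range is 70 − 6 = 64 to 70 + 6 = 76 days.

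**ALT-led case.** ALT reaches 5xULN at V1 or V2 and the recheck follows 15 days later. Since 15 > 14, the mandated sample can show whether the persistence limb is met.

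**AST-led case.** Take, as an illustration, AST at 6xULN and ALT at 4xULN at V1.
- ALT is below the 5xULN trigger.
- ALT is also below twice its V0 value if V0 ALT was above 4/2 = 2xULN, which entry criteria allow.
- Neither trigger fires, so the next scheduled AST is at V2, 70 days later (64 to 76).
- Relative to the limit: 70/14 = 5 times.
- Time beyond the limit: 70 − 14 = 56 days (64 − 14 = 50 to 76 − 14 = 62).

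The same holds for a rise first seen at V2.

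**Where the gap does not apply.** V0 to V1 is 4 × 7 = 28 days, and section 4.1.4 stops treatment after V3.

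**Each section 10.1 limb against what is mandated.**

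| Limb | What it needs | Mandated source |
|---|---|---|
| ALT or AST > 8xULN | One value | Full panel at each scheduled visit |
| ALT or AST > 3xULN with bilirubin or INR | One panel | Full panel at each scheduled visit |
| ALT or AST > 3xULN with symptoms | One value plus clinical findings | Full panel at each scheduled visit; symptoms from clinical follow-up |
| ALT > 5xULN for more than 2 weeks | A second timed ALT | 15-day recheck |
| AST > 5xULN for more than 2 weeks | A second timed AST | None before the next scheduled visit |

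Only the last row lacks a mandated, timed source. If the patient does reach the 15-day visit because ALT rose, the text guarantees ALT there and is silent on AST.

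**The case against.** The strongest reply is that AST is not left unwatched. Section 6.3 requires a safety evaluation to be repeated when the investigator rates an abnormality clinically relevant, and followed until it normalises or is explained. Section 9.7.3 has clinically significant laboratory results reported as adverse events, and section 6.1.6 follows those until resolved or stable. Section 6.3.2 allows extra safety samples at any time. Section 10.1 is not an algorithm either: its list is expressly not exhaustive, and it lets the investigator withdraw a patient for any laboratory abnormality that makes continuing unwise. A site can obey both sections, so this is a mismatch in coverage and not a flat contradiction. The affected group is also narrow, and the documents give no frequency for it.

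Most of that stands and sets the limits of the point. A reader might infer four stronger things that the documents do not support:
- That AST persistence has no measurement behind it. Section 6.3 makes repeat and follow-up mandatory once the result is rated clinically relevant.
- That AST will go unassessed for 10 weeks. It can; a careful investigator may well repeat it sooner.
- That the peak limb and the bilirubin or INR limb share the gap. They can be judged on the panel drawn at each scheduled visit.
- That the recheck sample excludes AST. Section 5.3.7 guarantees ALT but does not forbid other tests.

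The reply does not supply a time limit. The section 6.3 repeat depends on the investigator's rating, names no analyte and gives no interval. Its reach to AST is also not clear-cut: Table 1 lists AST under safety assessments, whereas Table 8 labels it an efficacy test. DSMB data reviews, held every 50 patients (section 6.4.4), cannot stand in for a timed recheck in one patient. For ALT the protocol chose not to rely on discretion.

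**Conclusion.** The point holds for the AST persistence limb only. An AST above 5xULN first seen at V1 or V2, with ALT below both triggers, has no mandated timed repeat for 70 days (64 to 76), against a criterion that turns on 14 days. When ALT does trigger the 15-day visit, AST is not guaranteed to be measured at it.

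This rests on three assumptions. Visits are taken to keep to schedule. No discretionary repeat is taken to occur, since none is timed. Sections 5.3.7 and 10.1 are taken to be unchanged in protocol version 5.1, which the SAP cites; the text reviewed here is version 5.0. How many patients would be affected cannot be estimated from the documents.

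The mismatch is specific, bears on patient safety and is cheap to remove, so it should be corrected even though no efficacy inference depends on it. SAP section 3.5 reports that 247 patients had already been randomised, so a change protects only those still on treatment.

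**What to change.** Reconcile sections 5.3.7 and 10.1 so that the mandated recheck and the withdrawal criteria it refers to agree on which transaminases are covered. The sponsor's clinicians should decide which text governs and at what levels; this review takes no position on either.

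The cost is amendment wording and possibly a few additional safety visits. The recheck draw is already in the protocol, and the central laboratory already measures AST at every scheduled visit.

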## 6. Safety Assessment

### 6.1 Adverse Events

#### 6.1.1 *Definitions accroding to ICH guidelines*

- **Adverse event:** Any untoward medical occurrence in a patient or clinical investigation subject administered a medicinal product and which does not necessarily have a causal relationship with this treatment. An AE can therefore be any unfavourable and unintended sign (including an abnormal laboratory finding), symptom, or disease temporally associated with the use of an IMP, whether or not considered related to the IMP.
- **Adverse reaction of an IMP:** All untoward and unintended responses to an investigational medicinal product related to any dose administered.

All adverse events judged by either the reporting Investigator or the Sponsor as having a reasonable causal relationship (i.e. possible/probable) to a medicinal product qualify as adverse reactions. The expression reasonable causal relationship means to convey in general that there is evidence or arguments to suggest a causal relationship.

#### 6.1.2 *Collection*

The condition of the patients will be monitored throughout the study. Subjective symptoms reported spontaneously by the patient as well as signs observed by medical staff will be recorded in the source records and the eCRF.

Any AE (including laboratory test abnormalities, intercurrent illnesses or injuries, and/or study procedures related AE) reported spontaneously by the subjects, or observed by the Investigator, will be recorded in the trial database.

Any untoward medical event, which occurs from the time of signed Informed Consent to the time of first IMP administration, will be classified as “non treatment-emergent AE”.

#### 6.1.3 *Intensity Rating*

The intensity of an AE will be rated as follows:

- Mild: no interference with the subject's daily activities and does not require mandatory corrective/symptomatic treatment.
- Moderate: moderate interference with the subject's daily activities and/or requires minimal medical intervention or corrective treatment required.
- Severe: major and unacceptable interference with the subject's daily activities and requires mandatory corrective/symptomatic treatment, possible hospitalization.

#### 6.1.4 *Causality Rating*

The causal relationship of an AE to the IMP will be rated as follows:

- Unrelated: Clearly and incontrovertibly due only to extraneous causes, and does not meet criteria listed under unlikely, possible or probable.
- Unlikely: Does not follow a reasonable temporal sequence from administration of the IMP, or is most likely related to another etiology than the trial drug such as the patient's clinical state, environmental factors or other therapies.
- Possible: Follows a reasonable temporal sequence from administration of the IMP, and/or a causal relationship cannot be excluded and remains likely.
- Probable: good reason (such as clear-cut temporal association with improvement on cessation of the IMP or reduction in dose, or reappears upon (accidental) rechallenge, or follows a known pattern of response to the IMP) and sufficient documentation to assume a causal relationship.

#### 6.1.5 *Action Taken*

The action taken with the IMP for an AE will be rated as product withdrawn, temporary interruption, or dose not changed. AEs requiring therapy will be treated with recognized standards of medical care to protect the health and the well-being of the patient.

#### 6.1.6 *Outcome*

The outcome of an AE will be rated as recovered, recovering, sequelae, not recovered, fatal or unknown. The Investigator will follow up any AE until it is resolved or until the medical condition of the patient is stable. All relevant follow-up information will be collected.

For AEs that are ongoing at the last visit, the Investigator will make thorough efforts to document the outcome in the eCRF, until 28 days after end of study treatment for AEs considered by the Investigator as unrelated or unlikely related to study treatment, and until the database lock for AEs considered by the Investigator as possibly or probably related to the study treatment.

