## 6.2 Serious Adverse Events or Reactions

### 6.2.1 Definitions

A Serious Adverse Event (SAE) is any untoward medical occurrence or effect that at any dose:

- results in death;
- is life-threatening (at the time of the event);
- requires in patient hospitalization or prolongation of existing hospitalization;
- results in persistent or significant disability/incapacity;
- is a congenital anomaly/birth defect;
- or is an important medical event.

**Death:** the death of a patient enrolled in a clinical study is per se not an event, but an outcome. An AE resulting in a fatal outcome must be fully documented and reported, including if the death occurred after treatment end, and regardless of the causality relationship of the death to the IMP. The cause of the death is usually the AE. If the cause cannot be determined, the case will be considered an unexplained death.

**Life-threatening:** an AE that places the patient, in the view of the initial reporter (Investigator), at immediate risk of death from the AE as it occurred, i.e. it does not include an AE that, had it occurred in a more severe form, might have caused death.

**Hospitalization:** an AE requiring an unplanned inpatient hospital admission, including at least an overnight stay. Of note: when standard practice for liver biopsy requires overnight hospitalization, this shall not be considered as an adverse event.

**Disability:** a substantial disruption of a person's ability to conduct normal life functions.

**Important medical event:** an important medical event that may not result in death, be life-threatening, or require hospitalization may be considered as a SAE when, based upon appropriate medical judgement, it may jeopardize the patient and may require medical or surgical intervention to prevent one of the outcomes listed in the definition. The concept includes AEs which suggest a significant hazard, contraindication or precaution for use, occurrence of malignancy or development of drug dependency or drug abuse.

**Overdose:** an overdose of an IMP is the accidental or intentional administration of a dose higher than the highest dose under clinical investigation. An overdose will be documented and reported to the safety officer (SO) in the same way as a SAE even if no toxic effects were observed.

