### 6.2.2 Immediate reporting

The Investigator will immediately, i.e. within 24 hours from first knowledge, report any SAE occurring during the study to the safety officer (SO) acting on behalf of the Sponsor of the study:

STRAGEN SERVICES S.A.S, [name]  
[contact], [contact],  
Email:

The Investigator will complete in English and sign a SAE Report Form and transmit it to the SO by email or telefax not later than 24 hours after the first knowledge of the SAE. The SO acknowledges the receipt of the SAE information by email to the investigational site within one working day. In the absence of email acknowledging the receipt or in case of issue in sending the fax or email, the Investigator shall contact the SO by any means for ensuring the receipt of SAE information at the earliest opportunity.

Any follow-up information will be reported to the SO and to the Sponsor as soon as it becomes known, with the same process and timelines as described here above for initial reports. As per Article 17 of the European Directive 2001/20/EC, the Sponsor will ensure that all relevant information about SAE and suspected serious unexpected adverse reactions (SUSAR) is recorded and reported to the national CA in all Member States concerned and to Ethics Committee within the applicable timeframe.

Serious adverse events occurring after the last study visit will only be reported if the Investigator believes that the event may have been caused by the IMP or a protocol procedure.

Hospitalization for a diagnosis or therapeutic procedure planned before study enrolment but performed after the enrolment should not be considered for SAE and should be reported in eCRF in concomitant procedures page.

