### **6.3 Safety Variables**

All safety variables will be primary ones. Safety evaluations will be completed as given in section 9.7 and as indicated below.

The Investigator will rate all safety variables as to clinical relevance or not. In case of a clinically relevant abnormality, the safety evaluation will be repeated. If the abnormality is confirmed and clinically relevant, it will be recorded as an AE term in the eCRF. The abnormality will be followed up until the value has returned to normal or an adequate explanation is found.

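### Protocol 6.2.1 and 6.2.2 conflict on reporting an unrelated death after the last visit, and the causality filter in 6.2.2 can start inside the SAP's 28-day TEAE window

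*Protocol*

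**What the plan says.** **Deaths and SAEs.** Protocol 6.2.1 says that a fatal AE "must be fully documented and reported, including if the death occurred after treatment end, and regardless of the causality relationship"; the relationship meant is that to the study drug. It gives no end date. Protocol 6.2.2 first asks for any SAE during the study within 24 hours, without a causality condition, and for follow-up information on it as it becomes known. It then says: "Serious adverse events occurring after the last study visit will only be reported if the Investigator believes that the event may have been caused". The suspected cause has to be the study drug or a protocol procedure. No exception is made for fatal events.

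**What the analysis counts.** SAP 4.5.6.2 defines a TEAE as an event from the first dose to 28 days after the last dose. SAP 5.3.2.1 tabulates serious and fatal TEAEs. SAP 5.3.2.4 only lists later events. Protocol 9.7.2 says that SAEs and deaths will be listed and summarised whatever their emergence class and relationship to treatment.

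**Timing of the last visit.** Protocol 5.3.6 places V4 four weeks after the end of treatment. The synopsis and Tables 1 and 2 allow 3 days either side of each visit, counted from V0. After early withdrawal, 5.3.5 asks for V4 only where it can be done.

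**Follow-up of AEs.** Protocol 6.1.6 opens with: "The Investigator will follow up any AE until it is resolved or until the medical condition of the patient is stable". Its second paragraph limits how long the eCRF outcome is pursued when an AE is still open at the last visit. One limit reads: "until 28 days after end of study treatment for AEs considered by the Investigator as unrelated or unlikely related to study treatment". For events rated possible or probable, the end point is database lock instead. Section 10.1 adds: "In the case of withdrawal due to an AE the patient will be followed until resolution of the AE". Stabilisation with referral is its alternative end point. Section 6.3 says of a confirmed, clinically relevant abnormality: "The abnormality will be followed up until the value has returned to normal or an adequate explanation is found". The last two set no causality condition.

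**The concern.** A site that learns of an unrelated death after the last visit can satisfy 6.2.2 and breach 6.2.1 by staying silent. Two sites with the same case may therefore report differently.

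The second difficulty concerns the safety tables. A randomised comparison of serious and fatal events is sound when events are counted regardless of attribution, which is what protocol 9.7.2 intends. If collection becomes conditional on the investigator's causality judgement before the counting window has closed, the tables may omit events that the SAP says they contain. Patients who withdraw early and miss V4 are the most exposed. Withdrawal need not be balanced across arms, so any loss need not be balanced either.

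The AE follow-up wording is a smaller matter. Two sentences in 6.1.6 give different end points without saying which duty each governs, so sites may document the outcome of the same open event for different lengths of time.

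**Working it through.** There is no planned figure to reproduce. The check is arithmetic on days and a comparison of the rules.

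**Step 1: when V4 can fall.** Inputs: V3 at week 24, V4 at week 28, 3 days either side at each visit.
- V3 = 24 × 7 = day 168; V4 = 28 × 7 = day 196; nominal interval 196 − 168 = 28 days.
- Shortest: (196 − 3) − (168 + 3) = 22 days.
- Longest: (196 + 3) − (168 − 3) = 34 days.

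I take the last dose to be on the V3 date. Protocol 4.1.4 stops treatment after V3, and 7.1.1 has the patient take that day's dose after the V3 sample.

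**Step 2: how long the filter in 6.2.2 overlaps the SAP window.** If the last visit is *d* days after the last dose, the overlap is 28 − *d* days when *d* is below 28, and otherwise none.
- V4 at day 27: 28 − 27 = 1 day.
- V4 at day 22: 28 − 22 = 6 days.
- V4 at day 28 or later: no overlap.
- V4 missed, with an early V3 on the day of the last dose (*d* = 0): 28 days.

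The last case reads the last study visit as the last one attended. Section 6.2.2 does not say whether it means that or the scheduled V4.

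**Step 3: the rules side by side, for an event judged unrelated to drug and procedures.**

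| Onset of event | 6.2.1 (fatal only) | 6.2.2 | SAP |
|---|---|---|---|
| Up to the last visit | Report | Report | Counted if within 28 days of last dose |
| After the last visit, within 28 days of last dose | Report | Not reportable | Counted as TEAE |
| After the last visit, beyond 28 days | Report | Not reportable | Listed only |

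The first row is consistent. The second and third conflict for deaths. In the second row a non-fatal SAE is not covered by 6.2.1 at all, so no reporting rule secures an event that the SAP would count.

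**Step 4: the limit in 6.1.6.** Days left after V4 to document an unrelated AE still open there = 28 − (V4 − V3). Nominally this is 28 − 28 = 0. Over the windows it runs from 28 − 34 = −6 to 28 − 22 = 6. For a patient without V4 the last visit is earlier and more days remain, so the limit is not always empty.

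**The case against.** **The conflict over deaths is narrow.** The restricted sentence in 6.2.2 most naturally concerns events that begin after the last visit. An event that began earlier and later proved fatal is covered by 6.2.1, and by the follow-up duty in 6.2.2 if it had been reported as serious. A reader might infer that late deaths in general are recorded according to the investigator's view of causality. The documents do not support that: up to the last visit every SAE is reportable whatever its cause. What stands is a new, unrelated fatal event after that visit.

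**The period after treatment end in 6.2.1 may mean only up to V4.** That reading would remove the conflict between the two sections, but neither section states it. It would also leave the overlap in Step 2 untouched.

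**The protocol's own TEAE definition ends at the follow-up visit.** Under 9.7.2 the counting window and the filter meet, so the mismatch comes with the SAP's fixed 28 days. That is fair, but the tables follow the SAP, and the protocol's definition has no end point for a patient who misses V4.

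**Section 6.1.6 can be read coherently.** Its first sentence can be a general duty to follow the event, its second paragraph a limit on eCRF documentation, and 10.1 a specific rule for withdrawals. This is plausible and largely meets the point; what remains is that the division is not written down. A reader might infer that outcomes are lost in about half of patients. If both visit windows are taken as independent and uniform over 7 days, V4 falls on or after day 28 in 28/49 = 57% and earlier in 21/49 = 43%. Those figures describe assumed visit dates, not AEs that are unrelated, open and unstable at V4. An AE that is stable by V4 already meets the first sentence.

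**The effect on analysis is limited.** Events beyond 28 days are only listed. This holds, and it confines the effect on the tables to the second row in Step 3.

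**Conclusion.** The concern holds in two parts. First, 6.2.1 and 6.2.2 give opposite instructions for an unrelated fatal event after the last study visit. Secondly, the filter in 6.2.2 can open before the SAP's 28-day window closes, by 1 to 6 days when V4 is early and by up to 28 days when V4 is missed. Unrelated SAEs and deaths in that interval may then be missing from tables that protocol 9.7.2 presents as independent of relationship.

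The day counts assume a last dose on the V3 date. For withdrawn patients they also assume that the last visit is the last one attended and that it falls on the day of the last dose. The number of affected events cannot be derived from the documents.

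The wording of 6.1.6 is a lesser ambiguity: two sentences whose relation to each other and to 10.1 is not explained. It does not show that outcomes are systematically discarded, nor that all AEs need a single stop point. Efficacy, sample size and power are unaffected.

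**What to change.** - Reconcile 6.2.1 with 6.2.2 so that deaths fall under one rule, and say what the last study visit means for a patient who withdraws.
- Word the collection of SAEs and deaths so that, whatever the causality rating, it spans at least the SAP's window of 28 days after the last dose.
- State how the two paragraphs of 6.1.6 fit together and how they relate to 10.1 and 6.3. The stop point for following AEs is for the sponsor to choose.
- At the same time, align the 30-day follow-up in 3.9 and 4.1.3 with the four weeks used elsewhere, a difference of 30 − 28 = 2 days.

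The cost is protocol wording, and possibly a contact at day 28 for patients whose last visit came earlier. No analysis needs to be redesigned.
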